6.3 Visit 2: Baseline MRI session #1

Staff and participants will follow the fMRI Lab COVID-19 safety guidelines.

This session will occur at the fMRI laboratory on North Campus. This visit will follow the screening session by up to ~2 weeks, depending upon availability of the fMRI and TMS suite. During the visit, we will acquire baseline MRI data, including localization data using the n-back task. We will also obtain motor threshold in the adjacent TMS suite and give subjects an initial exposure to iTBS stimulation to ensure tolerability.

This session should last approximately 2 – 3 hours.

6.3.1 Safety assessment: We will review the subject's safety screening forms for fMRI and TMS to make sure nothing has changed since the initial assessment. We will also record sleep and ingestions of psychoactive substances (caffeine, alcohol, nicotine). We will prepare them for the MRI scan, ensuring that they remove all metal from their person (lockers are provided at the fMRI laboratory to store personal items such as wallets, cell phones).

6.2.2 MRI Image acquisition: Scanning will be performed at the UM Functional Magnetic Resonance Imaging Laboratory (fMRI Lab) on a 3T MR 750 scanner (Waukesha, WI) using a 32-channel coil.

When we position a subject in the scanner, head movement will be minimized through: (a) instructions to the participant; and (b) packing the head inside the head coil with a system of foam padding and pillows that we have found is well-tolerated by the participants, yet limits movement. Extra care will be taken to ensure that the participant's head is positioned as straight as possible since that eases the task of identifying landmarks used in positioning slices to be acquired in the fMRI scans. A mirror or MR-compatible goggle system projects the computer display output into the bore of the scanner. Stimuli are controlled and responses recorded either by E-Prime (PST, Inc., Pittsburgh, PA) or Presentation (Neurobehavioral Systems, Albany CA) lab software. Participants will wear a response claw on their hands with buttons in order to make button-press responses during cognitive tasks. The stimulus-presentation and response-collection systems have been tested to ensure that no artifacts are introduced and that there has not been an increase in the image-level noise. The goggle system may contain an eye tracking camera, which can permit the monitoring and possible analysis of eye movements during the scan. In addition, MR-compatible earphones may be used and physiological sensors may be attached. These sensors consist of a strain gauge, or strap that

goes around the torso, to measure respiration, and plastic finger cuff, to measure heart rate by plethysmography and CO₂ monitor (although latter may not be used if it is redundant with pulse oximeter). These non-invasive sensors are FDA-approved components (except for the CO₂ monitor) of the scanner, and the fMRI Center has begun to incorporate the physiological information into the acquisition sequences in order to improve image reconstruction. Because this is an area of data analysis that remains under development, we may not employ these sensors in all scans. Once in the scanner, subjects can communicate via intercom with the technician running the scanner in the control room. A window separates the control room from scanner room, which is sealed off from the outside by a light vacuum seal. In addition to the intercom system, subjects are given a squeeze bulb. They are informed that should they need to exit the scanner immediately or gain the attention of the technicians, they can trigger an alarm in the control room by squeezing the bulb.

After localizer scans, subjects will undergo 3 scans: 1) BOLD-weighted fMRI (EPI, TR=800 ms, FOV=23, slice=2.4mm, 96x96 matrix) for the n-back task (8 minutes); 2) BOLD-weighted resting state scan for 10 minutes to obtain data for functional connectivity analyses (eyes open, looking at fixation cross); 3) pseudo-continuous ASL (pCASL) sequence following the recommendations of the ISMRM consensus(75). Our pCASL implementation will use a 3D stack of spirals acquisition(76) with 6 interleaves (TR=5000 ms, TE=4 ms, BW=125kHz, FOV=22 cm) preceded by a 1800 ms labeling period and an 1800 ms delay to allow the label spins to clear the arteries and enter the capillary/tissue compartment. Two hyperbolic secant inversion pulses at 600 and 1300 ms after labeling will suppress background signals, after first 2 frames to permit collection of spin density images for quantification. We will acquire 20 pCASL control-label image pairs, which will be reconstructed to a 128x128 matrix. Since the excitatory effects of iTBS have been demonstrated to last up to 60 minutes,(30) data acquisitions will occur in the appropriate time frame to capture iTBS effects. The last scan in the sequence will be a high-resolution structural scan (SPGR) for image normalization, as well as a T1 scan in the same prescription as the BOLD scans to facilitate normalization.

The scans and acquisition parameters described here are representative of what will be employed, although the actual acquisitions may differ slightly. Power-monitoring software on the scanner will ensure total energy delivered to the subject will remain within FDA guidelines. Specifically, the specific absorption rate (SAR) will be not greater than: 1) 4 W/kg averaged over the whole body for any period of 15 minutes; 2) 3 W/kg averaged over the head for any period of 10 minutes; 3) 8 W/kg in any gram of tissue in the head or torso; 4) 12 W/kg in any gram of tissue in the extremities, for any period of 5 minutes.

6.2.3 Visit 2 TMS session: This session will follow the MRI session for visit 2.

6.2.3.1 Motor threshold: Motor threshold will be obtained to calibrate the intensity of stimulation delivered for the TBS TMS sessions. Motor evoked potentials (MEPs) elicited using biphasic posterior-anterior stimulation will be recorded from right first dorsal interosseous (FDI) using surface electromyography (Rogue Research, Montreal, Canada). The motor cortical hotspot will be defined as the site of stimulation in left motor cortex that elicits the largest, consistent response in the FDI with the coil oriented at 45 degrees to the coronal plane. Active motor threshold (AMT) will be obtained as the percentage of stimulator output that elicits an MEP of $\geq 200 \mu\text{V}$ peak-to-peak on ten out of twenty trials while the subject is contracting the FDI muscle at approximately 20% of their maximum.(77)

6.2.3.2 Trial run of iTBS: In order to see if subjects can tolerate iTBS, we will do a 2-3 minute run of iTBS to the dorsolateral prefrontal cortex (approximate location). If a subject cannot tolerate iTBS, they will be withdrawn from the protocol (but receive payment for the 2 visits they completed).

6.3 Visits 3,4,5, Combined TMS/MRI sessions

These sessions involve the experimental manipulation, using iTBS TMS prior to the MRI session, in order to test hypotheses described in the Aims. These visits will also occur at the fMRI laboratory, which houses the TMS suite, across the hall from the MRI magnet. Each TMS session will differ, depending upon how iTBS is delivered and what the subject is doing while receiving stimulation. The MRI sessions will be identical.

We will seek to test participants at the same time of day to reduce circadian variability, separated by 1 to ~4 days. We will also work to schedule the 3 sessions in the same week, avoiding Monday. Each session will last approximately 2-3 hours. Below, we describe what happens for each of the three visits.

6.3.1 Safety assessment: We will review the subject's safety screening forms for fMRI and TMS to make sure nothing has changed since the prior session. We will also record sleep and ingestions of psychoactive substances (caffeine, alcohol, nicotine). We will prepare them for the MRI scan, ensuring that they remove all metal from their person (lockers are provided at the fMRI laboratory to store personal items such as wallets, cell phones).

6.3.2 Neuronavigation for TBS sessions: To determine the site for stimulation, we will use neuronavigation, with structural and functional information to account for individual variability in recruitment of the FPN. BOLD mages acquired from the first MRI session (Visit #2) will be analyzed with standard methods to determine the activation of 2-back minus 1-back, and aligned with the subject's high resolution SPGR structural scan. These data will be transferred to the Brainsight Frameless system (Rogue Research, Montreal CA). For the dlPFC target, we will locate the junction of the anterior and middle third of the left middle frontal gyrus (MFG), which corresponds to Brodmann area 46,(78, 79), and within a zone that is 1/3 the length of the MFG, will search for the locus of greatest activation in BOLD activation (2-back minus 1-back, or 1-back minus 2-back) for each subject, using those coordinates as the site of stimulation. The Brainsight system will be used to identify the overlaying scalp position. For the vertex (control) target, we will locate the approximate vertex, according to standard 10-20 system, but in a region where no BOLD change is detected.

6.3.3 TMS session: We will deliver iTBS, which has been shown to increase cortical excitability,(30) using 3 pulses of stimulation at 50 Hz, repeated every 200 ms, for 2 sec trains, repeated every 10 sec, giving a total of 600 pulses in 190 sec. Stimulation will be delivered at 80% of AMT, which is within consensus recommendations for safety,(80) and used in published work.(81)

In counter-balanced order, subjects will receive one of three iTBS sessions on each of the 3 days: 1) Vertex stimulation and subjects will be instructed to maintain gaze on a fixation screen and rest; 2) dlPFC stimulation (from neuronavigated target described above, subjects will be instructed to maintain gaze on a fixation screen and rest; or 3) dlPFC stimulation augmented with an n-back task. A computer screen will display an n-back task, using the 2-back condition. Letters will appear for 0.5 sec every 2 seconds, and presentation will be synchronized with the iTBS stimulation, which will occur 0.5 sec before the onset of every 5th letter. Actual parameters may differ slightly when delivered in the experiment.

6.3.4 MRI session: MRI sessions will be identical to Visit #2. The MRI will follow immediately after the iTBS TMS session.

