This proposal will examine a particular type of TMS, known as theta burst stimulation (TBS), which has been shown to induce longer lasting effects than other forms of TMS, making TBS an important tool for therapeutic applications. While TBS provides relatively focal stimulation, effects on the brain occur through interconnected networks in ways that are poorly understood. Moreover, stimulation is highly state-dependent, and the use of TMS in most therapeutic settings, such as the treatment of depression, leaves mental state uncontrolled. Augmenting TMS therapy by inducing specific mental states is an attractive idea for improving therapeutic TMS, but the relevant knowledge base is sparse. To address this critical gap, this exploratory R21 proposal will examine the effects of TBS on specific brain networks and the interaction between TBS and mental state. We will test the broad hypothesis that when TBS is applied during a controlled mental state, network changes will be facilitated, compared to stimulation when mental state is uncontrolled. We will focus on the dorsolateral prefrontal cortex (dlPFC) and the associated fronto-parietal network (FPN), which subserves cognitive control -- the ability to flexibly adapt and regulate behavior, an ability known to be impaired in neuropsychiatric conditions such as depression and dementia. We will use an 'n-back' task tapping cognitive control and the FPN. We will employ a within-subjects design with 40 healthy subjects in 4 MRI sessions. Each MRI session will consist of blood oxygenation level-dependent (BOLD) fMRI during an n-back task, resting state BOLD fMRI to measure connectivity and resting state arterial spin labeling (ASL) MRI to measure cerebral blood flow (rCBF) and examine effects on resting activity level. BOLD activation during the n-back will identify the FPN and the target site for dlPFC TBS. After a baseline fMRI session, subsequent sessions over different days will entail TBS, immediately followed by an MRI session to assess the effects of stimulation. TBS will involve: 1) dlPFC stimulation by active iTBS (600 pulses) alone or 2) while simultaneously performing an n-back cognitive task or 3) vertex (control) iTBS stimulation, alone. The following aims will be pursued:

Population: Healthy control subjects with no significant mental health problems.

Site: University of Michigan

Study Duration: 2 years

Subject Participation Duration: 3-4 weeks

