1.3 State-dependency of TMS stimulation

A critical fact about TMS is that effects are highly state-dependent. The phenomenon known as 'metaplasticity' refers to neural plasticity modulated by prior activity in a neuron,(46) and an analogous process may occur with TMS.(47, 48) Extracellular recordings in animals have shown that increased visual cortical activity during excitatory TMS leads to greater post-TMS activity.(49) From the earliest days of TMS research in humans, it was noted that stimulation of motor cortex during active muscle contraction increased the size and number of descending volleys compared to stimulation when the hand was at rest.(50, 51) Since then, multiple examples of state-dependency have been described. For example, activating the ipsilateral hand during stimulation alters the response and coupling in the contralateral cortex during TMS to premotor cortex.(52) Directing attention to the contralateral hand during 5 Hz stimulation leads to larger MEP increases than when attention is directed to the ipsilateral hand.(53) Global changes in brain state, such as sleep, have demonstrated large effects, reducing the propagation of a single TMS pulse across the cortex when measured by surface electroencephalography.(54) In summary, multiple paradigms have demonstrated state-dependency of persisting TMS effects.

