In spite of what is known about the state-dependency of TMS, most therapeutic uses of rTMS do not systematically control the mental state of subjects during stimulation, although this is starting to change. rTMS has been combined with psychotherapy for depression.(16) Cue exposure in addiction(55) and exposure therapy for post-traumatic stress disorder(17) and OCD(8) have been paired with TMS. A commercial system that combines rTMS with cognitive training in dementia patients has been cleared for marketing in the EU, even though differential effects in a sham-controlled study were not found (n=26).(18) In spite of this work, there are no neuroimaging studies identifying the neural effects of state-dependency in paradigms relevant to therapeutic TMS. Examining motor function, Narayana and colleagues showed that, in 4-week training paradigm, subjects who received 5 Hz rTMS to the motor cortex while they performed a digit sequence task showed improved motor performance and increased cerebral blood flow, relative to sham stimulation, in regions linked to skill learning.(56) For cognitive control, many studies have examined neural effects of TMS delivered 'offline'(prior to neuroimaging) to a brain at rest,(39, 41, 57, 58) but virtually no work has examined offline, persisting effects of TMS delivered while a person is engaged in a task. These persisting effects of TMS interacting with brain state are critical to understand how this interaction could be harnessed for improved therapeutic effect. Thus, in **Aim 2 we will address the question: How does mental state modulate the effect of rTMS on FPN networks?**

The phenomenon of task state interacting with TMS has been used to target specific neural populations within a stimulated region, a paradigm known as 'TMS adaptation.'(59) It has been used to augment brain mapping studies of language processing(60) and higher level perception.(61) For example, Silvanto and colleagues(62) showed that when subjects viewed visual motion while receive inhibitory cTBS to direction sensitive neurons in V1/V2, performance after stimulation was impaired for the direction-sensitive neurons that were not activated during the passive viewing task. In other words, neurons engaged by the task appeared to be 'protected' from inhibitory cTBS. This motivates our **Aim 3, asking whether excitatory iTBS stimulation while the FPN is engaged would improve subsequent performance.**

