3.0 Study design

The study is a within-subjects design that will expose subjects to three TMS/TBS sessions, with each followed by an MRI session. The first MRI session, without TMS, will obtain baseline

measurements of FPN activation (providing the target for iTBS stimulation – see below), resting state connectivity and resting state cerebral perfusion. The subsequent 3 MRI sessions will occur in a counterbalanced order, acquiring the same imaging sequence, and following one of three iTBS sessions: 1) To dIPFC, without a concurrent task; 2) to vertex, without any concurrent task, and 3) To dIPFC, while subjects perform an n-back task.

Overview of experimental sessions

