8.0 Statistical analysis

Analyses described below represent planned analyses for primary and secondary measures. However, actual implementation of these analyses may differ slightly from what is described below, although the primary and secondary outcome measures will be as described.

Specific Aim 1: Localize neural effects of dIPFC iTBS

Primary outcome measures:

Primary outcome #1, BOLD activation: 2-back minus 1-back BOLD activation, voxelwise in FPN

Analysis Plan: MRI data analysis and strict quality control will use validated and established routines implemented in our laboratory. For processing BOLD images, we will use well-tested routines from FSL 5.0.1 and SPM12 for slice timing and realignment algorithms and spatial normalization (MNI-152) procedures implemented in VBM8. First-level analysis will use the general framework of the modified General Linear Model,(82) implemented in SPM12 with temporal convolution. For the *n-back* data the first-level design matrix will include regressors for 2-back and 1-back, iTBS/MRI session and 12 realignment parameters (including temporal derivatives of 6 realignment parameters). Second-level, between-subject analysis will consist of two-sided, one-sample t-tests for primary effects. For statistical inference across the FPN, and the entire brain, we will use topological false discovery rate (FDR)(83) providing corrected probabilities at $p<0.017$ ($0.05/3$, accounting for testing of 3 primary MRI measures). Given *a priori* hypotheses about FPN, a mask of activation (2-back minus 1-back, $p<0.001_{\text{uncorr}}$) at the group level, using all 4 MRI runs to provide the most representative mask, will be used as small volume correction.

(H1.1): iTBS to dlPFC, compared to vertex stimulation, will increase fMRI activation in the FPN during the n-back.

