two-compartment model, assuming gray matter T1 of 1400 ms. and 90% labeling efficiency. ROI analysis of the CBF images will occur in native space, using the FPN mask derived from n-back activation, warped to individual anatomy. A two-sided, paired t-test will test for effect of sessions, with $p < 0.017$ as alpha. Secondary analyses will be performed on 6 cm radius sphere at the site of stimulation, in addition to a whole brain, voxel-wise search for changes in gray-matter tissue, using topological FDR to correct for multiple comparisons to $p < 0.017_{\text{corr}}$.

(H1.3) iTBS to dlPFC, compared to vertex stimulation, will increase resting perfusion at the site of stimulation. PET studies of high frequency TMS have reported increased CBF at the dlPFC,(97) a finding which motivates our hypothesis here. However, a cTBS study by our co-investigator ([name]) also found *increased* CBF after supposedly inhibitory stimulation of dlPFC,(98) so we will be performing a two-tailed t-test here. While the primary analysis will focus on the site of stimulation, a secondary analysis will focus on the FPN network, defined by the n-back task.

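### Does allowing a task-activated or a task-deactivated dlPFC target, without stating how the direction is chosen, undermine the planned comparisons?

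*Combined protocol and SAP*

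**What the plan says.** The opening summary says that "BOLD activation during the n-back will identify the FPN and the target site for dlPFC TBS", and section 3.0 describes the baseline scan as giving "measurements of FPN activation (providing the target for iTBS stimulation". Section 6.3.2 has the operational detail. The Visit 2 scan is analysed for 2-back minus 1-back. Then, within a zone one third of the length of the left middle frontal gyrus, staff "will search for the locus of greatest activation in BOLD activation (2-back minus 1-back, or 1-back minus 2-back) for each subject". Section 6.3.3 uses this neuronavigated target for both dlPFC sessions. In the session with a concurrent task, "A computer screen will display an n-back task, using the 2-back condition".

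In section 8.0 the FPN region of interest is "a mask of activation (2-back minus 1-back", formed at group level from all four MRI runs. The session contrasts are two-sided and within subject. For rCBF, for example, "A two-sided, paired t-test will test for effect of sessions". The Aim 1 exploratory text adds a comparison of activated with deactivated targets, according to how each target was selected. It gives no model or alpha. Aim 2 reuses the imaging work-up on different sessions. Aim 3 uses a repeated measures ANCOVA with sex and age. Neither aim mentions target type.

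**The concern.** A peak in 2-back minus 1-back is a site that works harder under the higher load. A peak in the reverse contrast is a site whose signal falls under that load. Pooling the two mixes physiologically different targets, and the text gives no explicit rule for which one a subject receives.

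This seems to matter most for Aims 2 and 3. Section 1.3 cites animal work in which "increased visual cortical activity during excitatory TMS leads to greater post-TMS activity", and introduces Aim 3 as "asking whether excitatory iTBS stimulation while the FPN is engaged would improve subsequent performance". The task given during iTBS is the 2-back, so a deactivated target may not be engaged in the sense the rationale intends. The target also fixes the connectivity seed and the site of the rCBF measure. If the choice were loose, the pooled average could describe an unknown mix, another team could not reproduce the targeting, and the comparison of target types could be shaped after the data were seen.

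**Working it through.** **1. Is a rule missing?** 1-back minus 2-back is 2-back minus 1-back with the sign reversed, so both kinds of peak lie on one map. Analysing the scan for 2-back minus 1-back and then taking the greatest response in either direction are therefore compatible steps. With a fixed zone, a single criterion (greatest response) and two permitted signs, the natural reading is the largest absolute peak. Section 6.3.2 states no order of preference, threshold or fallback, so a rule of activation first and deactivation only if there is none would have to be read into it. The opening summary and section 3.0 are short descriptions. Section 6.3.2 itself uses the word activation for both signs, so they need not conflict with it.

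**2. Can target type bias a session contrast?** Let D be one subject's difference between two sessions. The target is fixed from Visit 2, before any experimental iTBS session, and is the same in both dlPFC sessions. The dlPFC v vertex contrast evaluates the connectivity seed at that same site in both sessions. Target type is therefore constant within a subject. It may change the size of D, but it cannot be unbalanced between the sessions compared. With a share q of deactivated targets, the pooled test addresses

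mean(D) = (1 - q) × d_act + q × d_deact,

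which is the average effect at the individualised site. In a simulation with opposite effects in the two types and a true average of zero, the pooled test rejected in 0.0162 to 0.0169 of runs against a nominal 0.0167, with 10% to 50% deactivated.

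**3. How large could dilution be?** The plan gives no power figure to reproduce. Its alpha is 0.05/3 = 0.0167, stated as 0.017. With 40 subjects and a two-sided paired t-test at 0.017, 80% power needs d = 0.53 SD. Assume d_act = 0.53, d_deact = 0 and unit SD within each type. Then

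standardised effect = (1 - q) × 0.53 / √(1 + q(1 - q) × 0.53²).

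| q | mean | SD | effect | power |
|---|---|---|---|---|
| 0 | 0.530 | 1.000 | 0.530 | 0.80 |
| 0.10 | 0.477 | 1.013 | 0.471 | 0.69 |
| 0.25 | 0.398 | 1.026 | 0.387 | 0.49 |
| 0.50 | 0.265 | 1.035 | 0.256 | 0.20 |

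The documents support neither these shares nor a nil effect at deactivated sites. The loss comes from q and the effects, so writing the existing rule out more fully would not alter it. This uses one summary value per subject and does not model the voxelwise FDR.

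**4. Can the share be predicted?** Model each subject's response in t units over 5 to 20 independent elements. With subject mean 1 and SD 1, the largest absolute peak is a deactivation in about 17% to 19% of subjects. With mean 2 it is about 3% to 4%, and with no true response 50%. An activation-first rule can be modelled only by adding a cutoff, and 3.1, the value tried, appears nowhere in the documents. At mean 1 and SD 1 it leaves 56% to 77% of subjects with no target at all, so it is not a workable alternative to compare against. These figures say nothing reliable about this trial.

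**5. Would fuller specification make the target-type comparison informative?** Suppose the effects are opposite (difference 2 × 0.53 SD) at alpha 0.05. With 36 v 4 subjects, a pooled-variance t-test has power 0.50 and a 95% half-width of 1.07 SD. A Welch test has about 3.7 df, power of about 0.35 and a half-width of 1.51 SD. With 30 v 10, power is 0.81 or 0.78 and the half-width 0.74 or 0.78 SD. If deactivated sites had no effect, the pooled-variance test has power 0.17 at 36 v 4 and 0.29 at 30 v 10. Naming a test does not cure small groups.

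**The case for a change.** The strongest case for a change is that the deactivated option is deliberate, since section 8.0 plans an analysis around it, so a selection step exists that the text does not fully describe. The neighbouring exploratory analyses (global brain connectivity, ALFF and the performance correlations) do give alpha levels, and this one does not. A sentence or two would settle the matter without new data or visits.

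Part of this stands. The direction rule is implied and not written, and the comparison is thinly described. But the gap is narrower than it looks. The comparison sits in the Aim 1 text on relations between the three MRI measures, so those outcomes and the dlPFC v vertex contrast are a fair reading. It is labelled exploratory, so flexibility there threatens no confirmatory claim. Nothing in the plan calls for it under Aims 2 or 3, and adding it would produce more imprecise estimates.

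The appeal to the rationale is also weaker than it seems. Section 1.3 motivates Aim 3 partly with a study in which engaged neurons appeared protected from inhibitory stimulation. Section 8.0 says under Aim 2 that directions are hard to predict and that less activation is possible. A site with lower signal in 2-back than in 1-back is also not shown to be inactive relative to rest.

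**Conclusion.** No change to the plan follows. Section 6.3.2 leaves unsaid that the strongest response of either sign is taken, and analysts applying it to a single contrast map would fill that gap sensibly. Whatever the mix of target types, the pooled within-subject tests keep their level and estimate the average effect at the individualised site. That conclusion rests on one target per subject, fixed at Visit 2 and used in both dlPFC sessions, as sections 6.3.2 and 6.3.3 imply.

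The cost of mixing is possible dilution: under the assumption of no effect at deactivated sites, power falls from 80% to about 69%, 49% and 20% at shares of 10%, 25% and 50%. Allowing both directions is a design choice the plan discloses and intends to explore. The exploratory comparison will probably be imprecise however it is specified, so a non-significant result should not be read as showing that the target types are equivalent.
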